### **9.3 Selection of Trial Population**

#### **9.3.1 Inclusion Criteria**

Eligible subjects must meet/provide **all** of the following criteria:

1. Written informed consent.
2. Completed the double-blind Treatment Period (Week 52) in Trial HZNP-HZN-825-301; subjects prematurely discontinued from trial drug in Trial HZNP-HZN-825-301 for reasons other than safety or toxicity can be included at the discretion of the Investigator after completing Trial HZNP-HZN-825-301 scheduled visits, including Week 52 assessments.
3. Willing and able to comply with the prescribed treatment protocol and evaluations for the duration of the trial.

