#### **9.3.2 Exclusion Criteria**

Subjects will be ineligible for trial participation if they meet **any** of the following criteria:

1. Anticipated use of another investigational agent for any condition during the course of the trial.
2. New diagnosis of malignant condition after enrolling in Trial HZNP-HZN-825-301 (except successfully treated basal/squamous cell carcinoma of the skin or cervical cancer in situ).
3. Women of childbearing potential (WOCBP) or male subjects not agreeing to use highly effective method(s) of birth control throughout the trial and for 4 weeks after last dose of trial drug. Male subjects must refrain from sperm donation and females from egg/ova donation for this same time period. Women are considered of childbearing potential if they are not postmenopausal and not surgically sterile (documented bilateral salpingectomy, bilateral oophorectomy or hysterectomy). A postmenopausal state is defined as no menses for 12 months without an alternative medical cause. A high follicle-stimulating hormone (FSH) level in the postmenopausal range may be used to

confirm a postmenopausal state in women not using hormonal contraception or hormonal replacement therapy. However, in the absence of 12 months of amenorrhea, a single FSH measurement is insufficient. Fertile male subjects must use a condom throughout the trial and for 4 weeks after the last dose of trial drug. A man is considered fertile after puberty unless permanently sterile by bilateral orchidectomy.

4. Pregnant or lactating women.
5. Any new development with the subject's disease or condition or any significant laboratory test abnormality during the course of Trial HZNP-HZN-825-301 that, in the opinion of the Investigator, would potentially put the subject at unacceptable risk.
6. Subjects will be ineligible if, in the opinion of the Investigator, they are unlikely to comply with the trial protocol or have a concomitant disease or condition that could interfere with the conduct of the trial.

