### **5.1 Full Analysis Set**

The full analysis set (FAS) will include all subjects who were enrolled (i.e., signed the ICF) and who received at least 1 dose or partial dose of HZN-825 in this extension trial. This will be the analysis set used for efficacy data analyses. Subjects will be analyzed according to the treatment group to which they were randomized in the previous trial and combine them as an “Overall” group as appropriate.

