### **5.2 Safety Analysis Set**

The Safety Analysis Set will include all subjects who received at least 1 dose or partial dose of HZN-825 in this extension trial. Subjects in this analysis set will be analyzed according to the group determined by the treatment that the subject received in the previous trial and overall, as needed.

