#### **9.1 Primary Efficacy Endpoint Analysis**

The primary efficacy endpoint will be the change from both Baselines (Trial Baseline and HZN-825 Baseline) in FVC% predicted at Week 52.

A mixed model for repeated measures (MMRM) will be fit to the data for descriptive purposes using observed change in FVC % predicted values from all planned post-Trial Baseline assessments (Weeks 16, 28, 40 and 52). The model will include the fixed covariates factors used for stratifying randomization (use of mycophenolate mofetil [yes/no] and presence of ILD [yes/no]) in the previous trial, the treatment received in the previous trial, treatment by Visit Week and Visit Week. The Trial Baseline value will be used as a continuous covariate. An unstructured covariance matrix will be used for the primary

analysis; if the model does not converge, other covariance matrices or descriptive statistics will be considered. The least squares mean (LS mean) difference in change from Trial Baseline to Week 52 in MMRM will be estimated from this model. For subjects with missing data at 1 or more time points, the available data will be included in the analysis. A similar process for the FVC % predicted for the change from HZN-825 Baseline will also be performed.

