## **10.3 Adverse Events**

### **10.3.1 Treatment-Emergent Adverse Events.**

Treatment-emergent adverse events (TEAEs) are defined as any AEs with an onset date on or after the trial drug start date and time (if known) and no later than 28 days after permanent discontinuation of trial drug.

Refer to the table, listing, and figure shell document for determination of TEAE status in adverse events that are missing critical AE date start and stop information. All TEAEs will be evaluated for both treatment periods (start from first dose at HZNP-HZN-825-301 and HZNP-HZN-825-302 to the end of HZNP-HZN-825-302). Imputed dates are only used for classification of TEAEs.

Prior AEs are defined as any AE with a start date prior to the date of first dose of study treatment. Prior AEs will not be summarized, but will be included in listings.

Follow-up AEs are defined as any AE occurring > 28 days after permanent discontinuation of trial drug for subjects who prematurely discontinue the study medication prior to 52 weeks (i.e. 392 days after first trial drug intake). Follow-up AEs will be identified in the listings as such. Related SAEs will be followed up until resolved or until the event stabilizes and the overall clinical outcome has been ascertained.

The Verbatim terms in the eCRFs will be mapped to preferred terms (PTs) and system organ classes (SOCs) using the current version of MedDRA. Adverse events will be graded for

severity using the Rheumatology Common Toxicity Criteria (RCTC) v2.0 [[Woodworth et al., 2007](#)].

For summaries by SOC, PT, and maximum severity, a subject will only be counted once for each SOC based on the maximum severity level reported for that SOC and once for each unique PT within that SOC level at the maximum intensity level reported for that PT.

For summaries by SOC and PT only, a subject will be counted at most once at the SOC level and at most once at each unique PT within the SOC level. Summaries presenting the frequency of TEAEs by SOC and PT will be ordered alphabetically by SOC and then, within a SOC, alphabetically by PT.

Event Adjusted Incidence Rate (EAIR) is defined as number of subjects with events / total subject-years. Subject-years for each subject will be calculated as (date of first event occurred – first dose date +1)/365.25. For subjects without an event, subject-years for each subject = (last day in study – first dose date +1)/365.25.

EAIR will be summarized by SOC and PT as needed for TEAE.

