Events for which the investigator did not record relationship to trial drug will be considered related to trial drug for summary purposes. However, by-subject data listings will show the relationship as missing. No imputation will be done in case of missing study treatment relationship for non-treatment emergent AEs.

The severity grade of events for which the investigator did not record severity will be categorized as “missing” for tabular summaries and data listings. The missing category will be listed last in summary presentation.

Treatment-emergent AEs will be summarized based on the Safety Analysis Set.

Summaries of the following types will be presented:

The number and percentage of subjects who experienced at least 1 TEAE will be provided and summarized by SOC, PT, and treatment group.

The following AEs summaries will be provided by SOC, PT, and treatment group. AE summaries followed by an asterisk(\*) will include the number of events and the corresponding incidence of events per PYE.:

- All TEAEs by maximum severity
- All treatment-emergent SAEs\*
- All treatment-related TEAEs\*
- All treatment-related TEAEs by maximum severity
- All treatment-related treatment-emergent SAEs
- All TEAEs meeting CRISS criteria
- All TEAEs leading to permanent withdrawal of any trial drug
- All TEAEs leading to death (ie, outcome of death)
- All follow-up adverse events
- All serious follow-up adverse events
- Subject incidence of AESIs: [REDACTED]

A brief, high-level summary of AEs described above will be provided by treatment group for the study treatment period and by the number and percentage of subjects who experienced the above AEs. All deaths observed in the trial will also be included in this summary. For the overall summary, the category of “TEAEs by maximum severity” described above will be replaced by AEs with severity > Grade 3.

The frequency of TEAEs occurring in > 5% of subjects in any treatment group will be summarized by treatment, primary SOC, and preferred term. A similar summary will be created for serious TEAEs occurring in > 3% of subjects in any treatment group by primary SOC and preferred term.

An adverse event plot will be created with AE incidences and risk differences (with corresponding exact 95% confidence interval) plotted together for the adverse events occurring in >5% of subjects in any treatment group. A similar plot will be created for SAEs occurring in > 3% of subjects in any treatment group.

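### Safety tables that start at the first dose of the parent trial include only subjects who entered the extension, so their 24-month percentages for death and safety withdrawal are too low.

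*SAP*

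**What the plan says.** SAP 10.3.1 evaluates adverse events over two windows: "All TEAEs will be evaluated for both treatment periods (start from first dose at HZNP-HZN-825-301 and HZNP-HZN-825-302 to the end of HZNP-HZN-825-302". The population is the same for both: "Treatment-emergent AEs will be summarized based on the Safety Analysis Set". SAP 5.2 defines that set: "The Safety Analysis Set will include all subjects who received at least 1 dose or partial dose of HZN-825 in this extension trial". The summaries listed in 10.3.1 include events leading to death and events leading to permanent withdrawal. The event adjusted incidence rate (EAIR) in the same section counts subject-years from a first dose date, without saying which trial's first dose is meant.

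SAP 10.3.3.2 tabulates liver test thresholds and potential Hy's Law cases. It also evaluates them from both baselines, as needed, with a denominator drawn from the Safety Analysis Set.

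Entry to 302 depends on what happened in 301. Protocol 9.3.1 requires this: "Completed the double-blind Treatment Period (Week 52) in Trial HZNP-HZN-825-301". Subjects who stopped 301 drug early "for reasons other than safety or toxicity can be included at the discretion of the Investigator", once they have finished the 301 visits. Protocol 9.3.2 excludes most new malignancies. It also excludes a new disease development or "any significant laboratory test abnormality during the course of Trial HZNP-HZN-825-301" where the Investigator sees an unacceptable risk.

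For efficacy, SAP 9.1 fits a repeated-measures model to change in FVC % predicted from the 302 baseline and adds: "A similar process for the FVC % predicted for the change from HZN-825 Baseline will also be performed". The Full Analysis Set is likewise limited to subjects "who received at least 1 dose or partial dose of HZN-825 in this extension trial".

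**The concern.** The clock for the 301-origin tables starts a year before the selection that decides who is in them, and that selection depends on the year's events. A subject who died in 301, or stopped its drug for safety, cannot be in the Safety Analysis Set. Each subject who is in the set contributes a first year in which those two outcomes were impossible. This is immortal time.

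Protocol 7.2 gives long-term safety and up to 24 months of treatment as reasons for the trial. The exposure categories in SAP 10.1 also run to 24 months, so readers will take the 301-origin tables as two-year results. Death and stopping for safety are two of the outcomes that matter most in such a table. Protocol 7.1.3.5 names transaminase increase as an important identified risk, and a subject taken off 301 drug for it is missing from the 301-origin liver table. Neither document defines a set of all subjects dosed in 301, a delayed-entry rule, or a caveat about this selection.

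**Working it through.** The plan states no event rate, sample size or non-rollover rate, so there is no figure to reproduce. The structure comes from the sections cited above; every risk below is an assumption.

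**24-month percentage.** Let q be the yearly risk of death or safety withdrawal, equal in both years, and suppose everyone without such an event enters 302. Among all subjects dosed in 301, the 24-month incidence is 1 − (1 − q)². In the rollover-only table year 1 contributes no events, so the table shows q.

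| Assumed q | True: 1 − (1 − q)² | Shown | Shown / true |
|---|---|---|---|
| 3% | 1 − 0.97² = 5.9% | 3% | 0.51 |
| 5% | 1 − 0.95² = 9.8% | 5% | 0.51 |
| 10% | 1 − 0.90² = 19.0% | 10% | 0.53 |

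**Unequal years.** Keep the year-1 risk at 5%.
- Year-2 risk 2.5%: true 1 − 0.95 × 0.975 = 7.4%, shown 2.5%, ratio 0.34.
- Year-2 risk 10%: true 1 − 0.95 × 0.90 = 14.5%, shown 10%, ratio 0.69.

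**EAIR, if calculated for these events from the first 301 dose.** Let λ be a constant yearly hazard. Each rollover adds one event-free year. Year 2 then adds 1 − e^(−λ) events over (1 − e^(−λ))/λ years. The rate shown is (1 − e^(−λ)) / [1 + (1 − e^(−λ))/λ].
- λ = 0.05: 0.0488 / (1 + 0.9754) = 0.0247, which is 0.49 of the true rate.
- λ = 0.02, 0.10 and 0.20: ratios 0.50, 0.49 and 0.48.
- Year-1 hazard 0.05, year-2 hazard half or double that: 0.0124 against 0.0377 (ratio 0.33), and 0.0488 against 0.0741 (ratio 0.66). The true rate here is events over both years divided by time over both years.

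Starting the clock at the first 302 dose gives (1 − e^(−λ)) / [(1 − e^(−λ))/λ] = λ. The 302-origin rate is therefore not diluted by an event-free year.

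**Liver.** Year-1 elevations in subjects who rolled over are counted. Those that led to stopping 301 drug for safety, or to exclusion as an unacceptable risk, are not. The documents do not give 301's stopping rules or counts, so the direction is clear but the size cannot be calculated.

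**FVC.** Let s be the share of 301 subjects who did not roll over, and D the amount by which their mean change was worse than that of rollovers. The rollover mean differs from the all-subject mean by s × D. With s from 10% to 30%:
- D = 2 to 8 points: rollovers look better by 0.2 (0.10 × 2) to 2.4 (0.30 × 8) points.
- D = 0: no difference.
- D = −4: rollovers look worse by 0.4 to 1.2 points.

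The documents do not fix s or D.

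**The case against.** **The 302-origin results carry the main objective.** The primary safety objective runs from Day 1 of the extension, and Protocol 9.5.3.1.2 starts the treatment-emergent period there. Those tables contain no event-free year, and SAP 9 says that comparisons and p-values are descriptive. This limits the consequence and means no error rate is at stake. It does not repair the 301-origin window, which the SAP adds, because a descriptive percentage can still be wrong.

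**Rates are not clearly planned for the affected events.** SAP 10.3.1 attaches rates per person-year to serious events and treatment-related events, not to the death and withdrawal tables. EAIR is produced only as needed. This stands: the firm finding concerns percentages, and the EAIR figures apply only if that rate is computed for these events from the first 301 dose.

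**A reader might infer that all cumulative safety tables are too low.** The documents do not support that. A subject can have a non-fatal serious event, an event of special interest or a liver elevation in year 1, continue, and be counted. The crude percentage with any event need not be too low, because rollovers are followed longer. There is likewise no reason to drop serious events from the 301-origin tables; doing so would discard real data.

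**A reader might also infer that the two-year FVC change is biased toward stability.** Selection is certain, but its direction is not shown. Protocol 9.3.1 admits subjects who stopped 301 drug for reasons other than safety, which covers lack of efficacy. Protocol 9.4.9 lets therapy begun for deterioration during 301 continue, so some subjects who worsened are expected to roll over.

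**An all-treated analysis reaches beyond the 302 population.** The SAP supports the 302 study report, so adding subjects who never entered 302 is an integrated analysis. That is fair. It is a reason to define the set explicitly, and it weighs more against a pooled FVC model than against the safety tables.

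**Conclusion.** The point holds for deaths and safety-related permanent withdrawals in tables that start at the first 301 dose. Year 1 is free of both by eligibility, so the 24-month percentages are too low. With constant yearly risk they show about half the true value, for example about 5% against 9.8% at an assumed 5% a year. With a year-1 risk of 5%, the ratio ranges from about 0.34 to 0.69 as year-2 risk goes from half to double. Any EAIR for these events counted from the first 301 dose would be diluted similarly.

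The direction follows from the entry criteria as long as some such events occurred in 301. The size rests on assumed risks and on everyone without such an event entering 302, because the documents give no 301 figures. The 301-origin liver tables lack cases that led to stopping in 301, by an unknown number.

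The finding does not extend to non-fatal serious events, to other events that allowed rollover, or to 302-origin tables. For FVC change from the 301 baseline it supports only a caution: possible selection bias of unknown size and direction.

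**What to change.** In SAP 10.3.1 and 10.3.3.2:
- Define a set of all subjects who took at least one active dose in 301, whether or not they entered 302. Produce the 301-origin death, withdrawal and liver summaries for the QD and BID groups on that set.
- Keep the 302 Safety Analysis Set for every summary that starts at 302 Day 1.
- Tie the first dose date in the EAIR to the window being reported.

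If only the 302 set is to be used, start the death and safety-withdrawal tables at the first 302 dose. Show 301 deaths, safety withdrawals and non-rollovers by arm beside them. Keep serious events in the tables.

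In SAP 9.1, label the FVC change from the 301 baseline as conditional on rollover, with possible selection bias of unknown size and direction. A pooled model of 301 and 302 visits is an option but not a requirement: it mixes double-blind with open-label data and assumes that missing values are missing at random.

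The cost is SAP text, one added analysis set and extra programming on 301 data that the sponsor holds. The cumulative figures for death and safety withdrawal will look less favourable.

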#### **9.5.3.1.2 Documentation of Adverse Events**

AEs that are ongoing at the completion of HZNP-HZN-825-301 and/or occur prior to dosing on Day 1 will be considered pre-dose AEs. The TEAE reporting period begins with administration of the first dose of fipaxalparant (HZN-825) in this extension trial on Day 1 and continues until 4 weeks after the last dose of fipaxalparant (HZN-825) or premature discontinuation. All pre-dose AEs, TEAEs and AEs during the Follow-up Period must be recorded in the source documents and on the subject's eCRF. If a subject discontinues due to an SAE, that subject will be followed per Section [9.5.3.1.5](#).

If the Investigator observes an SAE after trial completion that he/she believes was possibly caused by fipaxalparant (HZN-825), the Investigator will report this SAE using the procedures described in Section [9.5.3.1.5](#). The Investigator is responsible for collecting and documenting the outcome of AEs/SAEs.

If specifically requested, the Investigator may need to provide additional follow-up information, such as discharge summaries, medical records, or extracts from the medical records. In this case, all subject identifiers, except for the subject number, will be blinded on the copies of the medical records before submission to the Sponsor.

Detailed information regarding all SAEs must also be recorded on the Serious Adverse Event Reporting Form. Whenever clinically appropriate, the Investigator should group together into a single term the signs and symptoms that constitute a single diagnosis. For example, cough, rhinitis and sneezing might be grouped together as “upper respiratory infection” if the Investigator is confident of the diagnosis.

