### 7.3 Baseline Definition

Unless otherwise specified, Baseline is defined as the last non-missing observation prior to the first dose of trial drug at the baseline visit as specified. For observations occurring on the same date as the first dose of trial drug where time is not collected but the protocol specifies the evaluation must occur prior to administration of trial drug, the result occurring on the day of first trial drug administration will be considered as Baseline.

Two types of Baselines are defined as below:

- Trial Baseline, defined as the latest non-missing measurement prior to the first dose of HZN-825 (BID) in this HZNP-HZN-825-302 extension trial.
- HZN-825 Baseline, defined as the latest non-missing measurement prior to the first dose of trial drug (QD, BID, Placebo) in HZN-825-301.

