### **10.1 Extent of Exposure**

Exposure to HZN-825 in HZN-825-302HZNP-HZN-825-302 will be descriptively summarized by treatment group: drug exposure, measured as duration of treatment (days treated), is the number of days on treatment based on the first and last days of treatment with the study medication (last day of study medication – first day of study medication + 1). This will be based on the trial drug dispensation CRF page.

Summary statistics will be provided for the duration of exposure to study medication (days) by treatment group. Additionally, a categorical breakdown of duration of treatment will be provided, including the following categories: 0 – 3 months, > 3 to 6 months, > 6 to 9 months, and > 9 to 12 months, > 12 to 15 months, > 15 to 18 months, > 18 to 21 months, > 21 to 24 months.

Summary statistics will also be presented for the total number of HZN-825 doses and total dose administered by treatment group.

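### The added TEAE window from the first 301 dose counts PLC/BID's placebo year as treatment-emergent and roughly halves malignancy rates (minor; the protocol's 302 TEAE result is unaffected)

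*SAP*

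**What the plan says.** - **Two windows.** SAP 10.3.1: "All TEAEs will be evaluated for both treatment periods (start from first dose at HZNP-HZN-825-301 and HZNP-HZN-825-302 to the end of HZNP-HZN-825-302". The same section places the TEAE summaries on the Safety Analysis Set.
- **One population.** SAP 5.2: "The Safety Analysis Set will include all subjects who received at least 1 dose or partial dose of HZN-825 in this extension trial". Membership therefore requires having got through 301 and into 302.
- **What starts the 301 clock.** SAP 7.3: "HZN-825 Baseline, defined as the latest non-missing measurement prior to the first dose of trial drug (QD, BID, Placebo) in HZN-825-301". Placebo is one of the 301 trial drugs. SAP 4.2 defines the PLC/BID group as placebo in 301 and 300 mg BID in 302.
- **Entry rule.** Protocol 9.3.2, criterion 2, excludes a subject with "New diagnosis of malignant condition after enrolling in Trial HZNP-HZN-825-301". Successfully treated basal or squamous cell skin carcinoma and cervical cancer in situ are excepted.
- **Rates.** SAP 10.3.1 defines EAIR as subjects with an event over subject-years, counted from first dose to first event or to the last day in study. It is planned by SOC and PT as needed. Separately, events per PYE are planned for treatment-emergent SAEs and for treatment-related TEAEs.
- **Protocol definition.** Protocol 9.5.3.1.2: "The TEAE reporting period begins with administration of the first dose of fipaxalparant (HZN-825) in this extension trial on Day 1". Footnote 17 of the SAP's appended schedule agrees.

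**The concern.** Protocol 7.2 gives long-term safety, with up to 24 months of drug, as a purpose of this extension. The tables that start at the first 301 dose are where a reader would look for it. In those tables the PLC/BID column mixes a placebo year with a drug year and calls both treatment-emergent. Any Overall column inherits part of that mixture. If an event is less frequent on placebo, both columns understate its rate on drug.

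Malignancy has a different problem. The entry rule removes subjects diagnosed in 301, yet those who remain each bring about a year of 301 person-time to the denominator. The longer window would then appear to show a lower malignancy rate simply because of who was allowed in.

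**Working it through.** The plan states no figure to reproduce. The documents give no sample size by group, allocation ratio, event rate or dropout rate, so h, c, r and p below are assumptions, shown over ranges.

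**Step 1: which first dose the EAIR clock uses.** SAP 10.3.1 does not name the trial. A 302 Day 1 at Week 52 is 301 Day 52 × 7 + 1 = 365. For a first event on 301 Day 100, the 302 dose would give (100 − 365 + 1)/365.25 = −0.72 subject-years. In the longer window the first dose must therefore be the 301 dose.

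**Step 2: placebo share of person-time.** With one year in 301 and t years in 302, the placebo share in PLC/BID is 1/(1 + t).

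- t = 1: 1/2 = 0.50.
- t = 0.5: 1/1.5 = 0.67.

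If PLC/BID is a fraction p of subjects and t = 1 in all groups, the placebo share of Overall is p/2.

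- p = 1/3 (equal groups): 0.167, or 1/6.
- p = 0.20: 0.10.
- p = 0.50: 0.25.

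**Step 3: effect on a rate.** Let r be the placebo event rate divided by the drug event rate, with t = 1. Relative to the drug rate, PLC/BID shows (1 + r)/2, and Overall with equal groups shows (5 + r)/6.

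| r | PLC/BID | Overall |
|---|---|---|
| 0.33 | 0.67 | 0.89 |
| 0.5 | 0.75 | 0.92 |
| 1 | 1.00 | 1.00 |

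**Step 4: malignancy EAIR.** Let h be the yearly hazard of a non-excepted malignancy in 302 and c the yearly rate of other dropout.

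- 302 person-years per entrant: P = (1 − exp(−(h + c)))/(h + c).
- The 301 year adds 1 person-year and no events, so the 301-start rate divided by the 302 rate is P/(1 + P).
- Example: h = 0.10, c = 0 gives P = (1 − exp(−0.10))/0.10 = 0.952, and 0.952/1.952 = 0.488.

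| h | c = 0 | c = 0.20 |
|---|---|---|
| 0.01 | 0.499 | 0.474 |
| 0.05 | 0.494 | 0.469 |
| 0.10 | 0.488 | 0.464 |
| 0.20 | 0.475 | 0.452 |

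The halving hardly depends on h. It comes from one event-free year set against at most one year at risk.

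**Step 5: counts rather than rates.** For an outcome that can only occur in 302, n (%) is the same in both windows. For example, at h = 0.10 with no other dropout it is 1 − exp(−0.10) = 9.5% in each.

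**The case against.** The strongest reply is that the protocol-defined safety result is intact. TEAEs from 302 Day 1 are still reported, all safety summaries are descriptive, and the PLC/BID label tells the reader that this group began on placebo. EAIR and the safety set's Overall grouping are both planned only as needed. The table shells, which are not public, may carry labels or footnotes. All of this stands, and it limits the weight of the point. It does not change which events and which person-time enter the 301-start rates.

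Some stronger readings are tempting, but the documents do not support them.

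- **That PYE is undefined and SAE rates could be wrong by a factor of two.** SAP 10.1 says "Exposure to HZN-825 in HZN-825-302HZNP-HZN-825-302 will be descriptively summarized by treatment group", which might suggest dividing two years of events by one year of exposure. Nothing directs that. SAP 8.1 gives a treatment period for each Baseline, and Protocol 9.6.4 bases the AE rate on follow-up during dosing. Only a sentence tying PYE to those periods is missing.
- **That deaths and safety withdrawals are distorted.** Inclusion criterion 2 admits early drug stops only "for reasons other than safety or toxicity can be included at the discretion of the Investigator". However, no rate is planned for the death and withdrawal tables, and their n (%) are about the same in both windows. TEAEs are dated by onset, so an event with onset in 301 can still lead to death or withdrawal in 302.
- **That liver results are biased in the same way.** Exclusion criterion 5 mentions "any significant laboratory test abnormality during the course of Trial HZNP-HZN-825-301", but this applies only where the investigator judges the risk unacceptable. The liver summaries from HZN-825 Baseline are counts and percentages, planned as needed. The documents give no way to size an effect.
- **That the risk-difference plots share the fault.** SAP 10.3.1 names neither a window nor a reference group for them. That is a separate matter, and the shells may settle it.

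**Conclusion.** The point holds, as a minor one, for the added window only. In AE tables starting at the first 301 dose:

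- PLC/BID's placebo-year events are treatment-emergent. About half of that column's person-time is placebo with a full 302 year, and about one sixth of Overall with equal groups.
- The EAIR of a non-excepted malignancy is about 0.45 to 0.50 of the 302 rate.

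The first result rests on the assumed group shares and a full 302 year. The second rests on a constant hazard, other dropout of 0 to 0.20 per year, and no malignancy with onset dated in 301 but diagnosed in 302. The entry rule does not exclude that last case, because it turns on diagnosis while TEAEs are dated by onset.

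A reader might infer that the trial's safety conclusion is compromised. It is not: the window in Protocol 8.1 and 9.5.3.1.2 is kept, and the affected tables are supplementary and descriptive.

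**What to change.** In SAP 10.3.1, for any AE summary that includes 301 time:

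1. Start the TEAE clock, EAIR subject-years and PYE at the first HZN-825 dose: 301 Day 1 for QD/BID and BID/BID, and 302 Day 1 for PLC/BID. Alternatively, show PLC/BID's placebo year in its own column, outside Overall.
2. State that the PYE denominator is the SAP 8.1 treatment period matching the events counted. Under the first option in item 1, that is the 302 period for PLC/BID.
3. Report malignancy rates for the 302 window only. Item 1 does not cure this for QD/BID and BID/BID, whose 301 year is still free of entry-barring diagnoses.
4. Label 301-inclusive tables: *302 entrants only; not 24-month risk*.
5. Keep 301-onset events that lead to death or withdrawal during 302 in the summaries, in a row of their own where the new clock would drop them. SAP 10.3.1 otherwise lists prior AEs without summarising them.

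The cost is SAP wording, footnotes and table shells. It uses only data on 302 entrants that the SAP already plans to use. The downside is unequal follow-up, about 24 months for QD/BID and BID/BID against about 12 for PLC/BID, so 301-inclusive tables should be presented as person-time rates rather than n (%).
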